RESEARCH PROTOCOL

Title	Effect of GLP-1 receptor agonists on trabecular bone score and visceral adiposity in postmenopausal women with type 2 diabetes mellitus.
Principle Investigator/Co- investigators	PI: [name] Co-Investigators: [name], [name], [name], [name], [name], [name], [name] [name], [name]
Abstract	 Postmenopausal women with diabetes mellitus have a higher risk of osteoporotic fractures, with significant associated mortality and morbidity. Osteoporosis is underdiagnosed in diabetes, as the bone mineral density (BMD) as currently measured is often normal despite underlying abnormalities. The trabecular bone score (TBS) is a novel modality to assess bone microarchitecture and accurately assess fracture risk in patients with diabetes. Due to increased co-prevalence of osteoporosis and diabetes mellitus, the potential effects of antidiabetic medications on fracture risk assume importance. Based on findings in animal studies, we hypothesize that GLP-1 receptor agonists increase TBS in postmenopausal women with type 2 diabetes mellitus (T2DM). We propose a prospective non-randomized case-control study by enrolling 48 patients (24 in the GLP group and 24 in the non GLP group). DXA scans, markers of bone formation, and resorption, and selected inflammatory markers will be assessed at baseline, six months and one year. We expect to see a significant improvement in TBS in the GLP group as compared to the non GLP group. We also expect to see a decrease in bone resorption markers, inflammatory mediators, and visceral adiposity and an increase in bone formation markers in the GLP group as compared to the non GLP group.

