Study Design	This is a prospective non-randomized study of one year duration. A total of 48 (24 in the GLP group and 24 in the non GLP group) postmenopausal females will be enrolled in the study. This study design will allow us to study the effects of GLP-1 receptor agonists on bone metabolism (formation and resorption); and bone microarchitecture (TBS) and also provide evidence regarding the potential role of visceral adipose tissue in bone metabolism in postmenopausal women with T2DM. All UMMC providers in the division of endocrinology will be briefed about the study and all the participants will be drawn from the UMMC Endocrinee, Family Medicine, and Internal Medicine clinics. The treating providers will have sole discretion in the choice of medications to be used for the management of each patient's type 2 diabetes mellitus. Patients who are enrolled in the study will be placed in the GLP group if they are on GLP-1 receptor agonists (for the treatment of their diabetes mellitus as decided by their endocrine provider) or in the non GLP group if they are not on GLP-1 receptor agonists. Throughout the study, the management of the each patient's T2DM will be according to standard of care as decided by the treating provider, for both the groups. Methodology: Eligible participants will be identified by designated Research
	The treating provider will independently make the decision regarding the treatment of the patient's diabetes mellitus (whether GLP-1 receptor agonist or other medication needs to be started or not), then the treating provider will enquire if the patient is interested in participating in the study.

	If the patient is interested, the treating provider will notify the research personnel who would see the patient promptly in the privacy of the examination room and then explain to the patient about the study in detail (objectives, design, tests involved and follow up, etc.) and seek their consent. Once consent is obtained then the research personnel will enroll the participant to the appropriate group (GLP vs non GLP) based on the medications prescribed by the treating provider. The research personnel will coordinate with radiology to schedule the baseline, 6 months and 1 year DXA scan. We will obtain research blood draws at baseline, 6 months and 1 year utilizing the same venipuncture done for routine clinical labs at these visits.

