	the three DXA scan amounting to a total of 30\$ for the entire study. Please see the Schedule of events document for a detailed description of study procedures.
Inclusion Criteria	Criteria that will identify the study population -A diagnosis of Type 2 Diabetes Mellitus -Postmenopausal female -Age >55 years - Hemoglobin A1c between 7 and 10 within 6 months of the first visit.
Exclusion Criteria	List all exclusion criteria* -A diagnosis of Type 1 Diabetes mellitus -History of GLP-1 receptor agonist/DPP4 inhibitor use -eGFR <30 ml/min in the last 3 months -History of pancreatitis -Documented personal or family history of medullary thyroid cancer -Documented history of treatment with anti-osteoporosis agents - Documented secondary osteoporosis -Documented presence of prosthesis or devices in the spine -Unwilling or unable to consent

Number of Participants/	
Records to be reviewed (anticipated)	48
	The primary outcome will be change in TBS from baseline to six months and one year after the initiation of a GLP-1 receptor agonist. TBS will be assessed by DXA scans done at baseline, six months and one year.
	The secondary outcomes are - Change in visceral fat mass (measured by DXA) at 6 and 1 year after starting GLP-1 receptor agonists as compared to baseline.
Outcome Measures	- Change in inflammatory markers and bone resorption markers (as measured by commercial assays) at 6 and 12 months after starting GLP- 1 receptor agonists as compared to baseline.
	- Changes in levels of sclerostin, osteocalcin, and P1NP (as measured by commercial assays) from baseline to six months and one year after starting GLP-1 receptor agonist.
	Statistical methods to assess changes in individual measures and possible correlations among different measures (e.g. TBS, visceral fat mass, and biomarkers) are described below.
Study Endpoints	Outcomes will be assessed at six months and one year and will be compared to baseline values.

	PHI to be accessed: Patient's medical record
	PHI to be collected:
	Name, Address, phone number and email address
	Medical record number
	Date of birth
	Race (African American or Caucasian)
	Duration of menopause (Years and months)
	Duration of T2DM (Years and months)
	Smoker (Yes/No) and duration
	Alcohol use (Yes/No) (Years and months)
	Presence of diabetic retinopathy (Yes/No)
	Presence of diabetic neuropathy (Yes/No)
	History of falls and/or fractures (Yes/No)
	List of anti-hyperglycemic medications
	List of current medications
	Weight
	Height
	BMI

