Barta da da da alub	Hip circumference
Protected Health	Waist circumference
Information (PHI)	Blood pressure
	Date of DXA scan
	Visceral adiposity index
	Subcutaneous adiposity
	Lumbar trabecular score
	Hemoglobin A1c (%)
	Low density lipoprotein (LDL)
	High density lipoprotein (HDL)
	Total cholesterol
	Triglycerides
	Microalbuminuria/Creatinine ratio
	Interleukin-1 (IL-1)
	Interleukin-6 (IL-6)
	Tumor necrosis factor-alpha
	C-telopeptide Sclerostin
	PINP
	Osteocalcin.
	RedCap will be utilized to record all study date. Access to study data
	will be restricted to members of the study team.

	Statistical analyses were designed in collaboration with [name], PhD (Statistics).
	Means and standard deviations of baseline, six month and one year TBS values will be reported. Changes in TBS will be analyzed using a linear mixed model contrasting the GLP and non GLP groups.
Statistical Methodology	Means and standard deviations of baseline, and 6 and 12-month values of visceral fat mass, IL-1, IL-6, TNF- α and C-telopeptide levels will be reported. Changes in TBS will be analyzed for any correlation the changes in visceral fat mass, levels of inflammatory mediators and C-telopeptide in the GLP and non GLP groups using linear or logistic regression as appropriate.
	Means and standard deviations of baseline, six month and one-year values of sclerostin, P1NP and osteocalcin will be reported and analyzed for any correlation to the changes in TBS in the GLP and non GLP groups linear or logistic regression as appropriate.
	Power analysis : The primary endpoint is the change in TBS at 6 and 12 months compared to baseline. From prior studies we expect a 10% increase in TBS (corresponding to 0.117 for human TBS) for the GLP group only. With a difference of 0.117 between 24 cases and 24 controls we have power of >0.8 and < 5% probability of type 1 error. The primary motivation for this pilot study is to assess effect sizes to support more accurate power calculations, to be used in an application for extramural funding to conduct a larger, definitive study.

	1) Kanis JA (2007) WHO Technical Report, University of Sheffield, UK: 66.
	2) https://www.iofbonehealth.org/facts-statistics#category-14 as accessed on 4/1/2019.

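### Aims 2 and 3: the plan specifies a GLP versus non GLP contrast for TBS only, and none for visceral fat mass or the seven biomarkers

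*Combined protocol and SAP*

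**What the plan says.** - **Specific Aim(s).** Aim 2 hypothesises that the drug lowers visceral fat mass, IL-1, IL-6 and TNF-alpha, with an associated fall in C-telopeptide. Aim 3 hypothesises that it lowers sclerostin, with an associated rise in osteocalcin and P1NP.
- **Abstract.** The expected secondary results are stated against the control group. The sentence ends with a decrease in "visceral adiposity and an increase in bone formation markers in the GLP group as compared to the non GLP group".
- **Study Design.** "This study design will allow us to study the effects of GLP-1 receptor agonists on bone metabolism (formation and resorption"), and also to give evidence on the role of visceral fat in bone metabolism. Groups follow prescribing: "The treating providers will have sole discretion in the choice of medications to be used for the management" of each patient's diabetes. Both groups have DXA and research bloods at baseline, 6 months and 1 year.
- **Outcome Measures and Study Endpoints.** Secondary outcomes are worded as change from baseline, with no comparator: "Change in visceral fat mass (measured by DXA) at 6 and 1 year after starting GLP-1 receptor agonists as compared to baseline". Study Endpoints repeats this: "Outcomes will be assessed at six months and one year and will be compared to baseline values". Outcome Measures adds that methods for change in the separate measures, and for correlations between them, follow later in the document.
- **Statistical Methodology.** For the primary outcome: "Changes in TBS will be analyzed using a linear mixed model contrasting the GLP and non GLP groups". For the Aim 2 measures: "Means and standard deviations of baseline, and 6 and 12-month values of visceral fat mass", the three cytokines and C-telopeptide, then regression of TBS change on the changes in these measures, in both groups. For Aim 3, visit values of "sclerostin, P1NP and osteocalcin will be reported and analyzed for any correlation to the changes in TBS", again in both groups.

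**The concern.** The hypotheses in Aims 2 and 3 are first about what the drug does to eight measures. Estimating that needs the change in treated patients set against the change in controls over the same period. The plan has the controls and schedules the measurements, but it attaches that comparison to TBS alone.

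The two things it does specify answer other questions. A correlation between marker change and TBS change describes how the two move together. A marker could track TBS equally well in both groups with no drug effect, or shift strongly under the drug without tracking TBS at all. Change from baseline in treated patients alone cannot separate the drug from time, regression to the mean, or the other diabetes care that continues at the provider's discretion.

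Followed exactly, the plan would leave the drug-effect part of both aims without a planned estimate. The study calls itself a pilot whose main purpose is to obtain effect sizes for a larger trial, and for an outcome measured as change that requires a group difference in change and an SD of change.

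**Working it through.** **1. What each measure receives in Statistical Methodology**

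| Measure | Aim | Visit means and SDs | Correlation with TBS change | GLP vs non GLP contrast |
|---|---|---|---|---|
| TBS | 1 | yes | not applicable | yes (linear mixed model) |
| Visceral fat mass | 2 | yes | yes | none |
| IL-1 | 2 | yes | yes | none |
| IL-6 | 2 | yes | yes | none |
| TNF-alpha | 2 | yes | yes | none |
| C-telopeptide | 2 | yes | yes | none |
| Sclerostin | 3 | yes | yes | none |
| P1NP | 3 | yes | yes | none |
| Osteocalcin | 3 | yes | yes | none |

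One fat measure plus seven biomarkers makes eight secondary measures; 0 of 8 has a contrast. No confidence interval is stated for any outcome, TBS included.

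**2. The plan's own figure.** The only power statement concerns TBS: power above 0.8 for a difference of 0.117 with 24 per group. No SD is given, so it cannot be reproduced. With a two-sided 5% t test it requires an SD of at most about 0.142 (0.117 / 0.142 = 0.82; 0.826 before rounding). No power or precision is stated for Aims 2 and 3, and the TBS figure does not bear on this point.

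**3. Precision if the contrast is added.** Simple comparison of mean change, in units of the SD of change, with equal SDs. Half-width of the 95% CI = t(0.975, 2n − 2) × √(2/n).

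- n = 24 per group (from the plan): 2.013 × 0.2887 = 0.58.
- n = 20 per group (assumed dropout; the plan gives none): 2.024 × 0.3162 = 0.64.

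The difference detectable with 80% power (two-sided 5% t test) is 0.83 SD of change at n = 24 and 0.91 at n = 20.

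**4. Multiplicity if each contrast were tested at 5%.** Assuming independence:

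- 8 contrasts: 1 − 0.95^8 = 0.34.
- 16 contrasts (both visits): 1 − 0.95^16 = 0.56.

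Related markers and repeated visits are unlikely to be independent. With an assumed common correlation of 0.5 the figures fall to about 0.25 and 0.37.

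**5. Baseline adjustment.** Assume no drug effect, a baseline imbalance of 0.5 SD and within-patient correlation r. None of these is in the documents.

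- *Stable imbalance* (group means persist): the unadjusted change contrast is about 0. The adjusted contrast is 0.5 × (1 − r) = 0.25, 0.15 or 0.05 SD at r = 0.5, 0.7 or 0.9.
- *Transient imbalance* (follow-up depends only on the observed baseline): the adjusted contrast is about 0. The unadjusted one is −0.5 × (1 − r) = −0.25, −0.15 or −0.05 SD.

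Neither version is safe in general when providers choose the treatment.

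**The case against.** The strongest reply is that this is a drafting omission in a pilot. Outcome Measures promises methods for the individual measures, the Abstract shows that the control comparison was intended, and the regressions are to be run in both groups, so tabulation by group is the natural reading. The investigators hold patient-level data, and for the Aim 2 measures they must compute changes anyway. The contrast can therefore be recovered at analysis.

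Most of that stands. It limits the severity and argues for a short fix. It does not supply the contrast: no other text does, and choosing the analysis of eight measures at two visits after the fact is what a plan should avoid.

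A reader might infer more than the documents support:

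- *That TBS has a planned CI and the secondary measures do not.* No CI is stated anywhere. What is particular to Aims 2 and 3 is the missing group contrast.
- *That the precision of the secondary comparisons could never be known.* Visit means and SDs alone would not let an outside reader rebuild a CI for change, but the investigators can compute it directly.
- *That the TBS correlations are misplaced.* The aims also hypothesise associations, and Study Design names the role of visceral fat in bone metabolism. The correlations serve that part of the plan and should stay.
- *That an adjusted analysis is the correct one.* The bias can run either way, as shown in the working.

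**Conclusion.** The point holds as a missing analysis: 0 of 8 secondary measures has a specified GLP versus non GLP contrast, although the aims hypothesise a drug effect on each and the Abstract expects a difference from controls. The count rests on the text alone and needs no assumption. The precision and multiplicity figures describe what the added analysis could deliver; they rest on 24 completers per group, equal SDs and, for the 0.34 and 0.56, independence.

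It should be fixed but does not threaten the study. The primary TBS analysis is unaffected and the required data are already scheduled. It would be going too far to say that Aims 2 and 3 cannot be answered from these data: the gap is in the planned analysis and not in the data collection.

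**What to change.** Add to Statistical Methodology that the linear mixed model used for TBS, with group, visit, group × visit and a patient random effect, will also be fitted to visceral fat mass and to each of the seven biomarkers. Report the GLP versus non GLP difference in change from baseline with its 95% CI, and the SD of change by group, at 6 and 12 months. Label these results secondary/exploratory. Report the same CI for TBS. Keep the planned correlations with TBS change.

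A version adjusted for baseline value and a few collected confounders (for example BMI, HbA1c and duration of diabetes) is an optional sensitivity analysis. If it is included, say that under baseline imbalance either version can be biased, depending on whether the imbalance is stable or transient.

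Costs: a short addition to the text and a little more analysis, with no new patients, visits or assays. Precision is limited, and several contrasts invite chance findings, so the results should be read as estimates and not as confirmatory tests. Confounding remains because providers choose the treatment, and the added model does not remove it.
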